5.2 EXCLUSION CRITERIA

Subjects cannot:

- Have a diagnosis of Down syndrome (Trisomy 21) or any genetic disease associated with abnormal body composition
- Be underweight or “at risk for underweight” with moderate weight loss, defined as a starting Body Mass Index (BMI) <10th percentile for age and sex (for those >20 years of age, defined as an absolute BMI < 18.5)²
- Have pre-existing abnormal intestinal function (e.g. protein-wasting enteropathy, fat malabsorption)
- Be unable to comply with both the recommended diet and activity interventions (as determined by study or treatment team)
- Have a history of prior chemotherapy or radiation for other cancers
- Be unable to complete the necessary radiology examinations with fully interpretable data (e.g. hip replacement and metal prostheses preclude evaluation by DXA)
- Be pregnant (to be confirmed by urine or serum pregnancy test as per institutional routine care for chemotherapy and radiology exams)

¹ COG = Children's Oncology Group. CCG = Children's Cancer Group

² Per the latest definition of Center for Disease Control and Prevention, underweight is defined for those <20 years of age as a BMI <5th percentile for age and sex and an absolute BMI <18.5 in adults >20 years of age. “At-risk for underweight” is a study-specific definition outlined above.

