1.0 GOALS AND OBJECTIVES

1.1 Hypothesis:

In pre-adolescents, adolescents, and young adults (AYA) diagnosed with NCI/Rome High-Risk B-precursor acute lymphoblastic leukemia (HR-ALL), reducing gains in adiposity (i.e. fat mass) will improve leukemia sensitivity to induction chemotherapy, reduce post-induction minimal residual disease (MRD), reduce fatigue and obesity-associated toxicities, and improve quality of life.

1.2 Primary aim:

In AYA patients newly diagnosed with HR-ALL, to quantify the impact of a personalized dietary and activity intervention to mitigate chemotherapy-induced body fat gain throughout the critical first month of treatment ("induction").

1.3 Secondary aims:

In AYA subjects newly diagnosed with HR-ALL:

1. To compare the rate of leukemia "positive" minimal residual disease (MRD) in the bone marrow at end of induction ($\geq 0.01\%$ mononuclear cells) in those who received the intervention as compared to a historical controls.
2. To assess adherence to, and feasibility of, implementing a personalized and comprehensive dietary and exercise intervention during the first month of intensive chemotherapy

1.4. Exploratory aims:

In AYA subjects newly diagnosed with HR-ALL:

1. To evaluate persistence or extinguishing of this effect over months of continued dose-intensive pre-Maintenance phases of chemotherapy
2. To characterize the direct impact as compared to baseline of the intervention on self- and family- reported quality of life (QOL) outcomes including fatigue, mood, social interaction, and cognitive impairment reported via the PedsQL questionnaire and Child and Adolescent Scale of Participation (CASP) following the induction phase and serially during dose-intensive phases of chemotherapy.
3. To quantify the effect of adiposity on the activity of leukemogenic JAK2/STAT3, PIK3K/AKT/mTOR, MAPK/ERK, and other signaling pathways in leukemia cells as determined by kinase phosphorylation.
4. To quantify the effect of adiposity and of the intervention on the metabolic activity of leukemia blasts and of adipocytes as assessed by IGF-1, other obesity-associated cytokine signaling pathways, adiponectin, leptin, free fatty acid synthesis and metabolism, and levels oxidative stress.

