4.0 SCREENING AND ENROLLMENT

4.1 SUBJECT IDENTIFICATION

Physicians who wish to enroll patients should first contact the local site's research coordinator to determine if the study is currently open to accrual. Patients with newly diagnosed HR-ALL greater than or equal to 10 years of age are to be identified for eligibility screening by the oncology care team and/or study investigators. Screening logs with a coded identifier are to be maintained by each site; for eligible subjects not enrolled, the reason should be recorded.

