5.0 PATIENT CRITERIA FOR ELIGIBILITY

The eligibility criteria listed below are to be interpreted literally. All clinical and laboratory data required for determining eligibility of a patient enrolled on this trial must be available in the patient's medical and research record which will serve as the source document for verification at the time of audit.

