This endpoint will be reported as the proportion of study subjects who adhere to proposed dietary and activity interventions. A threshold of 80% of RD and PT visits (combined, RD only, PT only) completed will determine feasibility of incorporating the intervention itself into induction therapy. Adherence to each component of the intervention will be further assessed using a threshold of 75% MET-minutes prescribed/completed and 75% of dietary adherence prescribed/actual intake (overall, and to each macronutrient group). Further exploratory analysis will examine which sets of activities and dietary recommendations afforded the greatest level of adherence and any trends toward adherence by age, sex, race, and/or ethnicity.

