15.0 RECORDS AND REPORTING

Research records will be maintained through paper study-specific case reporting forms (CRF). Research records for this study will be maintained in locked cabinets in the Clinical Trials Office (CTO) or institutional research offices accessible only to the investigators and study team. The master list linking subjects to their unique identifier will be kept in the regulatory binder locked in the CTO office and in a password-protected database. Regulatory binder and CRFs will be maintained primarily by the research coordinator with assistance from the PIs/investigators as needed.

Study results will be entered by each site directly into the secure REDCap database maintained by USC/SC-CTSI. At conclusion of the treatment portion of the study, screening logs with coded identifiers only will be provided from each site to enable assessment of selection bias (e.g. CONSORT diagram). The database will then be downloaded by the study PI for potential further secondary analysis and follow-up as indicated in Section 13.2 (“Study Closure”). The database will remain under unique password-protection and will remain strictly confidential. At the conclusion of the prescribed 5-year follow-up period (final study closure), all identifying information will be destroyed and the database will be preserved in a password-protected completely de-identified format for a minimum of six years as per CCI requirements at which time it will be destroyed.

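### Patients judged unable to comply are excluded and need not be counted, so adherence and feasibility may be overstated for HR-ALL induction by an amount the plan cannot show

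*Combined protocol and SAP*

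**What the plan says.** Secondary aim 2 (Section 1.3) is "To assess adherence to, and feasibility of, implementing a personalized and comprehensive dietary and exercise intervention during the first month of intensive chemotherapy". It is framed for young patients newly diagnosed with HR-ALL, without restriction to those expected to manage the programme.

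Section 5.2 lists among its exclusions those who would "Be unable to comply with both the recommended diet and activity interventions (as determined by study or treatment team". It gives no test or definition for that judgement. Section 5.0 adds: "The eligibility criteria listed below are to be interpreted literally". A patient so judged is therefore ineligible.

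Section 13.3 says the endpoint will be "reported as the proportion of study subjects who adhere to proposed dietary and activity interventions". Completion of 80% of dietitian (RD) and physical therapist (PT) visits "will determine feasibility of incorporating the intervention itself into induction therapy". Adherence is further judged against 75% of prescribed MET-minutes and 75% dietary adherence.

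On record keeping, Section 4.1 says "Screening logs with a coded identifier are to be maintained by each site" and "for eligible subjects not enrolled, the reason should be recorded". Section 15.0 says that, once the treatment portion ends, "screening logs with coded identifiers only will be provided from each site to enable assessment of selection bias (e.g. CONSORT diagram".

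**The concern.** The entry filter is a team's judgement of something close to what secondary aim 2 sets out to measure. Patients who fail it appear in neither the adherence nor the feasibility denominator, yet the feasibility conclusion is worded for induction therapy as a whole. A favourable result would describe patients not judged unable to comply, and could be read as describing HR-ALL induction patients generally.

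The plan anticipates selection bias and collects screening logs to assess it. The reason-recording rule, however, covers only eligible patients, so it leaves out those removed by this criterion. If the reason is not written down at screening, it may not be recoverable later. Section 13.3 presents the study as preparation for a randomized Phase III trial, whose planners would want to know which population the adherence and feasibility figures describe.

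**Working it through.** **1. The plan's own denominator.** Section 13.1 predicts 43-45 eligible subjects over three years, with more than 85% enrolled and evaluable. 43 × 0.85 = 36.55, which reproduces the stated figure of at least 36; 45 × 0.85 = 38.25 is consistent with it. The 43-45 are already eligible, so they say nothing about how many patients the compliance criterion removes. The 80% and 75% cut-offs come with no power or precision statement, so there is no feasibility calculation to reproduce.

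**2. Tracing an excluded patient through the records.**
- Section 5.2 with Section 5.0: judged unable to comply, hence ineligible.
- Section 4.1: a screening log is kept, but the duty to give a reason covers eligible patients only. This patient is not covered.
- Section 4.6: the eligibility checklist is completed before official enrolment, and the text does not require one for a patient who is never enrolled.
- Section 5.0: the duty to hold eligibility data in the record refers to enrolled patients.
- Section 13.3: denominators are study subjects. This patient is absent.
- Section 15.0: the logs are to support a selection-bias assessment, but nothing above ensures that they carry the reason this needs.

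**3. Possible size.** Let f be the rate among n = 36 enrolled subjects and k the number excluded only under this criterion. Counting every excluded patient as a failure gives

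rate among all otherwise eligible = f × 36 / (36 + k).

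Neither f nor k is in the documents; both are assumptions. For visit completion with f = 0.90, the numerator is 36 × 0.90 = 32.4:
- k = 0: 32.4/36 = 90.0% (no change)
- k = 2: 32.4/38 = 85.3%
- k = 5: 32.4/41 = 79.0%
- k = 8: 32.4/44 = 73.6%

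The 80% line is crossed when k exceeds 32.4/0.80 − 36 = 4.5.

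**4. Sensitivity to the assumed rate.** The smallest k that takes the figure below 80% is:

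| f among enrolled | smallest k | resulting rate |
|---|---|---|
| 80% | 1 | 28.8/37 = 77.8% |
| 85% | 3 | 30.6/39 = 78.5% |
| 90% | 5 | 32.4/41 = 79.0% |
| 95% | 7 | 34.2/43 = 79.5% |

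At f = 100%, k = 9 still gives 36/45 = 80.0%.

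The same formula applies to the proportion of subjects who meet a 75% adherence threshold: 80% of 36 becomes 75.8% with k = 2, 72.0% with k = 4 and 64.0% with k = 9. Section 13.3 sets no target for that proportion, so these values show dilution and not a pass or fail.

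**5. Which measure is most exposed.** Sections 6.1 and 6.2.4 attach RD and PT contacts to the initial hospital stay and routine weekly clinic visits. A patient unable to follow the diet or exercise plan could still complete many of those visits. Zero visits per excluded patient is therefore a worst case. Counting the same patient as non-adherent to diet or MET-minutes is closer to what the criterion says.

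**The case against.** The strongest case on the other side has five parts.

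- **A capacity screen.** The criterion says unable, and it sits beside other incapacity exclusions such as abnormal intestinal function. It may be a legitimate suitability screen and not a forecast of motivation. This stands, and is why the criterion need not be deleted.
- **Non-adherence after enrolment is kept.** Section 12.1 continues to follow subjects who refuse the intervention. Section 7.1 reduces or suspends activity for complications, and Section 7.2 keeps tracking data when the diet cannot be followed. Much non-adherence will therefore be observed. This also stands: enrolled subjects can still miss the 75% and 80% thresholds, so it would be wrong to call them a compliant group.
- **Visits are not adherence.** The feasibility threshold concerns visits, which overlap less with the criterion than the adherence measures do. This stands and limits the visit-based illustration to a worst case.
- **The estimand.** Reporting results in the eligible population is legitimate if that population is named. Resting the main feasibility statement on never-enrolled patients scored as failures would change the endpoint. This stands. If the Phase III trial kept the same criterion, the enrolled-subject figure would be the relevant one; the documents do not give its eligibility rules.
- **Logs already exist.** Section 15.0 states the intent to assess selection bias, and nothing forbids recording reasons for ineligibility. This stands only in part, because the stated rule in Section 4.1 stops short of what that assessment needs.

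A reader might go further and infer that feasibility is overstated, or that a handful of exclusions would reverse the feasibility conclusion. The documents support neither as fact. They give no count of exclusions and no completion rate. At 90% completion, falling below 80% takes 5 exclusions, that is 5 of 41 (12%) under this one criterion, each scored as zero visits.

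**Conclusion.** The point holds in conditional form. A team-judged criterion close to the adherence endpoint removes patients from the denominators, the conclusion is worded more broadly than the population studied, and the logging rule does not guarantee that the removals can be counted. Adherence, and to a lesser degree visit-based feasibility, may be overstated for HR-ALL induction patients.

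The likely direction is upward, but the size cannot be found from the documents and is nil if no one is excluded this way. The worst-case range of 85% to 74% rests on three assumptions: 36 enrolled subjects, 90% completion among them, and 2 to 8 excluded patients with no visits. Zero exclusions should not be taken for granted. In the pilot described in Section 3.0, more than half of the 14 patients in induction or consolidation named fatigue, poor balance or weakness, and energy levels as barriers to activity. That does not show that any of them would have been judged unable to comply.

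This is an inexpensive improvement that affects what secondary aim 2 can conclude. It does not affect the sample size or the primary analysis.

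**What to change.** 1. **Section 4.1:** record the reason for every screened patient aged 10-21 with new HR-ALL who is not enrolled, whether eligible or not, with 'judged unable to comply (5.2)' as its own code. The logs collected under Section 15.0 would then support the intended selection-bias assessment.
2. **Section 13.3:** keep the enrolled-subject analysis as the main one, report beside it the number excluded under this criterion, and limit the adherence and feasibility conclusion to patients judged able to comply.
3. **Section 13.3:** add a sensitivity figure, labelled a lower bound, in which patients excluded only under this criterion count as non-adherent or as not completing visits.

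The cost is one more code on an existing log, a somewhat longer log and a line or two of reporting, with no added patients or visits. The downside is that the feasibility statement may become narrower or less favourable.

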5.3 CONCOMITANT THERAPY

Patients may be receiving concurrent therapies including investigational agents for the treatment of their underlying malignancy.

5.4 CO-ENROLLMENT ON RESEARCH STUDIES

As per the Children's Oncology Group (COG) standard practice, this study is a behavioral intervention and does not include an investigational agent and is therefore not excluded from co-enrollment on COG trials. Moreover, the study behavioral intervention occurs during a treatment period (induction) where no COG or other research intervention is planned through the duration of this protocol. Of note, the relevant COG trial AALL1131 specifically outlines multiple concomitant therapies that are excluded but does not include behavioral interventions such as this one. For patient specimens, collection of samples for research will be coordinated closely with the clinical leukemia team; should a conflict arise for patient samples, priority will be first accorded to clinical care. Second priority will then be afforded to COG studies required for co-enrollment on COG therapeutic trials. Following both these uses, remaining sample will be obtained for this research study.

6.0 STUDY PLAN

6.1 SUMMARY OF STUDY PLAN

Pre-adolescent and AYA patients with newly diagnosed HR-ALL will have dietary and activity preferences assessed by a registered dietician (RD) and physical therapist (PT) at the start of induction.

Subjects will receive an individualized comprehensive dietary and physical activity plan. The RD and PT will devise a personalized dietary and activity intervention aimed at creating a minimum 10% caloric deficit each day (10% nutritional + exercise) throughout the four weeks of induction therapy. Adherence to the intervention will be assessed by the RD and PT at regular weekly intervals at routine clinic visits for chemotherapy and with home phone-calls between clinic visits. Home and hospital activity will also be recorded using a wearable electronic movement monitoring device (Fitbit ®) for all participants. A list of representative “menu” of possible activity interventions from which subjects may choose is provided as a separate Appendix. The primary efficacy of the intervention will be assessed in comparison to a recent historical control via determining the change in body fat percentage (and lean muscle) during induction as quantified by dual-energy x-ray absorptiometry (DXA). A key secondary aim will be the effectiveness of the intervention to reduce chemoresistance as evidenced by decreased prevalence of leukemia minimal residual disease (MRD) at the end of induction. MRD using multicolor flow cytometry is routinely assessed as a predictor of outcome in all patients with HR-ALL. Exploratory analyses will also examine biomarkers of the proposed mechanism including adiposity and intervention-related changes in leukemogenic signaling pathways, oxidative stress, and cellular metabolism. Parent- and subject-reported QOL assessments will consist of the PedsQL and Child and Adolescent Scale of Participation (CASP) surveys (see separate Appendix) and will be conducted pre- and post-induction and at two delayed time-points (mid-point of intensive chemotherapy [3 months from diagnosis] and at end of intensive chemotherapy phase [10 months from diagnosis] to assess the psychosocial benefits of the intervention.

6.2 TREATMENT PLAN

6.2.1 DIETARY INTERVENTION

The dietary intervention will be performed by an RD and is designed to achieve an at minimum $\geq 10\%$ daily caloric deficit to prevent fat gain along with a moderate fat (20-25%), high protein (20-25%), and low glycemic index/high fiber carbohydrate (45-55%) nutritional plan to prevent loss of lean muscle mass loss and to maintain micronutrient intake. The subject’s basal metabolic rate (BMR) will be calculated using the Schofield equation as per the World Health Organization recommendations (World Health Organization, Energy and Protein Requirements, Technical Report Series 724, 1985) with an activity factor of 1.3 (“for a well-nourished child at bedrest with mild to moderate stress”) applied to better estimate the subject’s resting energy expenditure (REE) from which to calculate the initial 10% caloric deficit goal. At the initial counseling session, the dietitian and family will determine which dietary technique is most likely to lead to dietary adherence. Dietary management tools will incorporate the My Plate (USDA) and the Traffic Light Diet tools to help educate families regarding portion size and eating habits. The RD will use a menu of common foods that meet the intake goals above as well as help families choose “exchanges” on the menu to personalize the menu options to maximize adherence. During the initial

hospitalization, the RD will visit with the subject to assess caloric and nutrient intake using a 3-day food intake log, counsel subjects and their families on nutrition and eating habits, and instruct how to monitor food intake using a simplified log. If available, and if the family so desires, the option will be available for families to use their personal cell phone or digital camera to take pictures of meals (before consumption and after consumption) to email to the RD to help guide the dietary intervention.

During subsequent weekly outpatient chemotherapy clinic visits (or if the subject remains hospitalized), the RD will follow-up with families on their perceived adherence and obtain intermittent dietary intake via 24 hour diet histories. Between clinic visits, the RD will also contact the family to provide reinforcement/motivation, answer questions, and obtain interval dietary history if necessary. Specific dietary recommendations for foods/drinks, meals, and snacks will be adjusted weekly in discussion with families to meet the daily caloric deficit and goal diet as described. The caloric goals may also be adjusted $\pm 5\%$ depending on insufficient/excessive weight or body composition changes. At the end of the acute intervention, the RD will discuss with the subject and family their dietary status and sustainable healthy eating behaviors.

6.2.2 PHYSICAL ACTIVITY INTERVENTION

The physical activity intervention will be performed by a PT who regularly works with children on therapy for ALL as well as generally with pediatric oncology populations. The PT will meet the subject and family surrounding the time of initial diagnosis. The PT will assess at baseline the subject's usual activity level, choices/preferences, and available activities at home once discharged. A key component of this baseline assessment, and of beginning the exercise program during the initial hospitalization, will be education provided to subjects and their families to allay concerns over potential muscle weakness and/or fatigue and demonstrate with positive reinforcement how to exercise safely during leukemia therapy. During the assessment, the subject's "rate of perceived exertion" (RPE) will be assessed to gain insight into the subjects thresholds for exercise intensity.

A target of 200 minutes/week will be set for a combination of "moderate" cardiovascular exercise and resistance training (36) with progressive goals based on adherence and capacity. As per latest guidelines from the American Heart Association, this weekly target may be accomplished with a minimum of 30minutes/day or divided into 15-minute sessions over the course of the day with the goal of daily exercise. To quantify the prescribed "moderate" exercise, metabolic equivalents (METs) were assigned to a variety of exercise modes from which the subject may choose, which best suit their preference and home capabilities (Appendix I). While the goal exercise prescription in METs is uniform for the intervention, the PT will work with the family and subject to outline an individual path to meet that goal based on the subject's physical capabilities, preference, and home availability. METs will be converted to "points" and the subject will be able to choose from suggested exercise modes with the appropriate number of minutes to meet daily and weekly "point" goals. Subjects will be asked if there are any additional activities/exercises they would like to include. If so, these will be added and the "points" (METs) calculated for them. Participants and their parents will be asked to record the selected mode and number of minutes performed on a study log (or calendar) and weekly total scores will be tabulated (METs-

minutes). For patients who do not complete (or do not bring) the study log, adherence will be assessed by the PT at the time of visit via subject self-report of days meeting activity goals. The following scale will be used: 0% (<1day/week), 25% (1-2days/week), 50% (3-4days/week), 75% (5-6days/week), 100% (7days/week). Reported activity must meet 100% of that recommended for each qualifying day. The exercise program will be progressive by nature such that the Daily Goal is increased each week depending on adherence, ability, and clinical condition.

All subjects will be provided a wearable electronic activity monitor (Fitbit®) to assist in recording home activity levels in minutes of activity; the Fitbit® has the important secondary benefit of providing visual reinforcement for the subject of their progress toward their Daily Goal as set by the study team.

